- 2) To determine whether any benefits of amisulpride are maintained by prolonging treatment beyond 12 weeks. Duration of stage 2 treatment was initially 24 weeks but was then reduced to 12 weeks, to enhance numbers still on treatment at their final assessment.

Secondary objectives

ATLAS will also investigate:

- (i) The associated risks of side-effects and serious adverse events;
- (ii) Compliance with allocated treatment;
- (iii) The effects of treatment on quality of life;
- (iv) The cost-effectiveness of amisulpride treatment.

Trial design

ATLAS is a pragmatic, randomised, 3-arm, double-blind placebo-controlled trial with two stages:

Stage 1 – an initial double-blind placebo-controlled stage to investigate efficacy and tolerability of oral amisulpride (arms A and B) versus placebo (arm C) over 12 weeks.

Stage 2 – a second double-blind stage investigating the effects of treatment continuation (arm A) versus switching to placebo (arm B) over a further 24 (initially, later 12) weeks.

Randomisation (3 Groups)

 Stage 1 – Weeks 1-12	 Stage 2 – Weeks 13-24 (or 36)	
(A) Amisulpride		Amisulpride
(B) Amisulpride		Placebo
(C) Placebo		Amisulpride

Outcome measures

Primary Efficacy Parameter – Brief Psychiatric Rating Scale

The first primary outcome measure is the Brief Psychiatric Rating Scale (BPRS), a widely used clinician-rated instrument for assessing positive, negative and affective symptoms in patients with psychotic disorders. The BPRS consists of 18 symptom constructs. Each item is assessed by the rater on a 7-point scale ranging from 1 (not present) to 7 (extremely severe). The total score is obtained by summing the scores from the 18 items. Scores thus range from 18 to 126, with higher scores indicating greater levels of psychopathy. The BPRS will be administered at baseline, at week 4, then again in weeks 10-12, week 16 and the final assessment (weeks 22-24 or 34-36). Change in BPRS score between baseline and the week 10-12 assessment and between the week 10-12 and final assessments are the trial's co-primary outcomes.

The second primary outcome measure is the proportion of patients withdrawn to open treatment by their physicians because of perceived lack of efficacy.

Secondary Efficacy Parameters

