(i) Extrapyramidal side effects (EPSE) measured with the Simpson-Angus Scale (SAS). The modified SAS used in ATLAS measures nine extrapyramidal signs: gait, arm dropping, shoulder shaking, elbow rigidity, wrist rigidity, leg pendulousness, glabellar tap, tremor and salivation, all of which are assessed by direct examination. Each item is rated on a scale of 0-4, with higher scores indicating greater severity of EPSE. The scale range of the modified SAS is thus 0-36. The SAS has been widely used to measure EPSE within clinical trials and will be administered at baseline, then again at week 4, weeks 10-12, week 16 and weeks 22-24 (initially 34-36). The change in SAS between baseline and week 10-12 and between week 10-12 and the final assessment (week 22-24 or 34-36) will be compared between groups to assess EPSE.

(ii) **Compliance** expressed as treatment discontinuation rates and as percentage of prescribed trial medication taken between weeks 1 and 10-12 and between weeks 13 and the final assessment will be compared in patient allocated to receive amisulpride and those allocated placebo.

(iii) Quality of life measured with the self-rated, 26-item, WHO Quality of Life Scale (WHOQOL-BREF) at baseline, 10-12 weeks and the final assessment. The WHOQOL-BREF includes two items about an individual's overall perception of their quality of life and health and questions assessing four

domains; physical, psychological, social and environmental well-being, which higher scores denoting a better quality of life.

A separate analysis plan for the cost-effectiveness will be drafted.

Sample size considerations

Because of the likely problems with recruitment and retention of patients with late-onset, schizophrenia-like psychosis, ATLAS included an initial Feasibility Phase following which, a pragmatic decision was made to reduce the target sample size from 200-300 to at least 100 participants, to be recruited by mid-2016. The statistical power calculations have been amended with the main emphasis being to answer the primary stage 1 question of whether 12 weeks of amisulpride provides worthwhile benefit. The minimal clinically relevant difference (MRD), given the potential hazards of antipsychotic drugs, is considered to be 5 points on the BPRS. We estimate that the standard deviation of BPRS scores will be 9 points. We are thus powering the trial on a minimal worthwhile standardised effect size of 0.56 (=5/9) standard deviations, a moderate treatment effect.

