5.2 Secondary endpoints:

The Simpson-Angus Scale (SAS) is used to see if amisulpride is having an effect on Extrapyramidal side effects (EPSE). The change in SAS scores will be plotted over time to see if there appears to be any increases over time. If the SAS scores remain constant over the assessment time points we can assume that amisulpride is having no effect on Extrapyramidal side effects.

Other continuous measures (EQ-5D and WHOQOL-BREF) will be analysed using the same methods specified in section 5.1, analysis of covariance.

5.3 Sensitivity analyses:

For assessment of change at week 12, analyses will be undertaken carrying forward week 4 assessments for patients with week 4 but not week 12 assessments. To evaluate the effect of compliance on treatment efficacy, the primary analysis will be repeated on a sub-group of participants who adhere to their allocated treatment arm but such analyses are prone to bias so will be interpreted appropriately cautiously.

5.4 Planned subgroup analyses:

Subgroup analyses will be limited to the same variables pre-specified in the protocol as minimisation variable used to balance randomisation:

- Age (60-69, 70-79, 80+)
- Gender
- Home circumstance (Living with spouse/partner, living alone, other)
- BPRS score (30-39, 40-49, 50+)
- Time since onset of symptoms (<6 months, ≥6 months)
- Previous antipsychotic treatment (No, Yes >1 month previously, Yes ≤28 days ago)

These exploratory subgroup analyses will be undertaken, appropriately cautiously, to investigate any influence of the prognostic factors. These subgroups will use standard test for significance of the parameter as an interaction in the repeated measures model.

Any deviations from this plan will be described in the final report.

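### SAP section 5.2 infers no extrapyramidal effect from flat Simpson-Angus scores without any between-arm estimate, and contradicts the comparison promised in section 3

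*SAP*

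**What the plan says.** The SAP treats SAS in two places.

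- **Section 3, Secondary Efficacy Parameters (i).** The modified SAS has nine items, higher scores are worse, and "The scale range of the modified SAS is thus 0-36". It is measured at baseline, week 4, weeks 10-12, week 16 and the final assessment. Change from baseline to week 10-12, and from week 10-12 to the final assessment, "will be compared between groups to assess EPSE".
- **Section 5.2, Secondary endpoints.** "The change in SAS scores will be plotted over time to see if there appears to be any increases over time". The next sentence gives the interpretation: "If the SAS scores remain constant over the assessment time points we can assume that amisulpride is having no effect on Extrapyramidal side effects". The section then moves on: "Other continuous measures (EQ-5D and WHOQOL-BREF) will be analysed using the same methods specified in section 5.1, analysis of covariance".

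Two further items bear on the point. Section 3 makes side-effect risk a secondary objective: "The associated risks of side-effects and serious adverse events". Section 5.4 lists, among the minimisation and subgroup factors, "Previous antipsychotic treatment (No, Yes >1 month previously, Yes ≤28 days ago", so recent antipsychotic use before entry is provided for.

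**The concern.** Section 5.2 does more than leave a method unstated. It fixes in advance a rule for declaring amisulpride free of an effect on extrapyramidal signs. The rule looks at whether scores change over time. It does not ask how they differ from placebo, sets no criterion for calling scores constant, and attaches no measure of uncertainty.

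The word that opens the following sentence (other continuous measures) places SAS outside the set given a model. An analyst who follows section 5.2 would plot and conclude. One who follows section 3 would compare arms, with no stated method. The two could reach opposite safety conclusions from the same data, in a trial that section 2 justifies by the need to weigh benefits against risks.

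**Working it through.** **1. The two passages side by side.**

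| | Section 3 | Section 5.2 |
|---|---|---|
| Quantity | Change in SAS within each stage | Change in SAS over time |
| Contrast | Between groups | None stated |
| Method | None stated | Plot |
| Basis for a conclusion | Difference between groups | Absence of visible change |

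**2. Why a flat course does not identify the effect.** Let a be the mean change in SAS on amisulpride and c the mean change on placebo over the same weeks. The effect is a − c. If amisulpride is flat, a = 0 and the effect is 0 − c = −c. This is zero only if placebo is also flat. If placebo falls by d points, c = −d, the effect is +d (worse on amisulpride), and a flat amisulpride course read by the rule gives no effect. A fall on placebo is possible if earlier antipsychotic effects wear off, since section 5.4 allows for use within the previous 28 days. The SAP does not say how many such patients are expected, so d is left as a symbol.

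**3. The plan's own power figure, to fix the likely arm sizes.** Inputs from sections 3 and 4: difference 5 BPRS points, SD 9, 100 patients, 10% drop-out so 90 assessed, two-sided 0.05. The SAP does not state the allocation ratio. Assuming three equal arms, A and B together have 90 × 2/3 = 60 and C has 90 × 1/3 = 30.

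- Standard error in SD units: √(1/60 + 1/30) = √0.05 = 0.2236.
- Power: Φ((5/9)/0.2236 − 1.96) = Φ(2.485 − 1.96) = Φ(0.525) = 0.700.

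This reproduces the stated 70%. A 45 v 45 split gives 0.750 and does not. So 60 v 30 is consistent with the plan, though it remains an assumption.

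**4. Scale of what non-detection could mean for SAS.** The SAP gives no SD for SAS, so results are in SD units and cannot be turned into points on the 0-36 scale.

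- Half-width of the unadjusted 95% CI: 1.96 × 0.2236 = 0.438 SD (0.444 SD with the t quantile on 88 degrees of freedom), about 0.44 SD either way.
- Power for a true difference of 0.4 SD: Φ(0.4/0.2236 − 1.96) = Φ(−0.171) = 0.43.
- Power for 0.5 SD: Φ(0.5/0.2236 − 1.96) = Φ(0.276) = 0.61.

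A proper comparison that showed nothing would therefore still leave moderate harm open. A plot judged by eye, with no interval, supports a claim of no effect still less.

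**The case against.** The strongest reply is that section 5.2 never withdraws the comparison in section 3. The plot can be read as additional to it. Section 4 also makes 95% CIs the default for estimates of amisulpride efficacy, and SAS sits under the heading of efficacy parameters, so an interval arguably comes with the section 3 comparison. On that reading the defect is one bad sentence and a missing method. This has force: a reader might infer that the SAP contains no placebo comparison of SAS at all, or that the plot is its only SAS analysis, and section 3 does not support that. Both statements hold for section 5.2 alone. The default interval does not rescue the rule, however, because the rule produces no estimate for an interval to accompany.

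Other stronger readings also go beyond the text:

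- **The plot pools the arms.** With 2:1 weights, +1 on amisulpride and −2 on placebo would average (2 × 1 − 2)/3 = 0 while the arms differ by 3 points. But section 5.2 does not mention pooling; it is silent on layout. If the plot is by arm and both arms are flat, the observed difference is near zero, and the remaining faults are the undefined criterion and the lack of an interval.
- **Patients with extrapyramidal effects drop out of the plot and flatten it.** This may happen, but the SAP gives no figure for it. Stopping treatment is not the same as stopping assessment, and section 4 keeps patients in their randomised arm whether or not they adhere. Informative loss would also trouble a model.
- **SAS does fall on placebo.** This is a scenario, not something the SAP documents.
- **0.44 SD is the size of the error.** It is the precision of a proper comparison. It does not say how often the flat-line rule would mislead.

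Finally, SAS is a secondary measure and the co-primary BPRS analyses are untouched. That limits the reach of the point without making the sentence sound.

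**Conclusion.** The point stands as an invalid inference rule together with an internal contradiction. Section 5.2 licenses a conclusion of no extrapyramidal effect from an absence of change over time, while section 3 calls for a between-group comparison that section 5.2 does not specify. Followed as written, the rule could report a real harm as absent, by the full amount d of any fall on placebo.

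No single figure measures the error, because the SAP gives neither an SAS standard deviation nor an expected placebo course. The half-width of about 0.44 SD is for scale only. It rests on equal arms, on the 90 assessed patients planned for BPRS, and on an unadjusted comparison; adjustment for baseline would narrow it by an amount that depends on a correlation the SAP does not give. The logical fault in the rule depends on none of these assumptions.

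**What to change.** 1. Delete the sentence in section 5.2 that assumes no effect when scores stay constant.
2. State how the section 3 comparison will be made, using the section 5.1 methods. SAS is measured at the same visits as BPRS, so they carry over directly.
   - Stage 1: repeated measures at week 4 and weeks 10-12, arms A and B together v C, adjusted for baseline SAS.
   - Stage 2: analysis of covariance, arm A v B, adjusted for week 10-12 SAS.
   - Say whether the minimisation factors are included as they are for BPRS. Either choice answers this point.
3. Report between-arm differences with 95% CIs, and limit any statement of no effect to the differences that the interval excludes.
4. Keep the plot, drawn by arm, as description only.

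The cost is a few lines of SAP text and one more run of models already planned. No extra data, visits or patients are needed.
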